7.0 Demographics, Baseline Characteristics, Medical History, and Prior/Concomitant Medications

Demographics, baseline or disease characteristics, medical history, and prior and concomitant medications will be summarized for the PP population and FAS. Categorical variables will be summarized with the number and percentage of subjects; percentages will be calculated based on the number of non-missing observations. Continuous variables will be summarized with descriptive statistics (number of non-missing observations, mean and standard deviation, median, minimum, and maximum).

7.1 Demographics and Baseline Characteristics

All baseline characteristic summary statistics and analyses are based on characteristics prior to the first dose of study drug.

Distributions of the continuous demographic and baseline characteristic variables will be summarized by treatment arm with the number of non-missing observations, mean, standard deviation, and median, as well as the minimum and maximum values. For the categorical demographic and baseline characteristic variables, the frequency and

percentages of subjects within each category will be summarized. The number of subjects with missing information will also be summarized.

The following demographic and baseline characteristics will be summarized:

Demographics:

- Age (years) and age categories age (< 40, 40 – 65, \geq 65 years)
- Gender (Male, Female)
- Race (Asian, Others)
- If Asian (Japanese, non-Japanese)
- Height (cm)
- Weight (kg)
- Tobacco user (current, former, never, unknown)
- Alcohol user (current, former, never, unknown).

Baseline and Disease-Related Characteristics:

- ECOG performance status (Grade 0, 1, 2)
- Relapsed or refractory
- Prior bone marrow involvement (Yes/No)
- Prior GI involvement (Yes/No)
- TLS risk category (High, Low)
- B-symptoms (Yes, No)
- Child-Pugh Classification (A, B, C)
- Number of prior regimens (1, 2, \geq 3)
- MIPI score (Low, Intermediate, High)
- Bulky disease (< 5 cm, \geq 5 cm)

7.2 Medical History

Medical history data will be coded using the Medical Dictionary for Regulatory Activities (MedDRA 23.0). The actual version of the MedDRA coding dictionary will be noted in the statistical tables and clinical study report. The number and percentage of subjects in each medical history category (by MedDRA system organ class and preferred term) will be summarized. The system organ class (SOC) will be presented in alphabetical order, and the preferred terms will be presented in alphabetical order within each SOC. Subjects reporting more than one condition/diagnosis will be counted only once in each row (SOC or preferred term).

7.3 Prior and Concomitant Medications

Prior and concomitant medications will be summarized by generic name. A prior medication is defined as any medication taken prior to the date of the first dose of study drug. A concomitant medication is defined as any medication that started prior to the date of the first dose of study drug and continued to be taken after the first dose of study drug or any medication that started on or after the date of the first dose of study drug, but not after the date of the last dose of study drug. The number and percentage of prior medication will be summarized. The number and percentage of subjects taking medications will be summarized by generic drug name based on the World Health Organization (WHO) Drug Dictionary for both prior and concomitant medications. The number and percentage of subjects who received CYP3A inhibitors and/or P-gp inhibitors, and/or antiplatelet agents and anticoagulants will be summarized by moderate/strong CYP3A inhibitors, moderate P-gp inhibitors and antiplatelet agents and anticoagulants.

In addition, post-treatment oncology medications will be summarized and/or listed. A post-treatment oncology medication is defined as any oncology medications taken after the discontinuation of study drug.

8.0 Handling of Potential Intercurrent Events for the Primary and Secondary endpoints

The primary endpoint of best overall response of CR will be analyzed based on the PP population and the secondary endpoints will be analyzed based on the PP/FAS population, as appropriate, the following potential intercurrent events (ICEs) will be considered:

- ICE1: Subjects with study drug discontinuation
- ICE2: Subjects with the use of other anti-MCL treatment

And will be handled for both primary and secondary endpoints based on the following strategy:

- The disease assessments after ICE1 and ICE2 will be used for the derivation of all endpoints.

9.0 Efficacy Analyses

9.1 General Considerations

PP population will be used for primary endpoint. PP population/FAS will be used for other efficacy endpoints, as appropriate.

All tests will be 1-sided at an alpha level of 0.025.

In the DLT assessment period, the first 6 study subjects enrolled was evaluated for the tolerability of the venetoclax and ibrutinib combination for a minimum of 5 weeks and at least 1 week of venetoclax dosing at 400 mg. DLT assessment committee along with ISM recommended that 'the study to be continued for full enrollment'.

The primary analysis will be performed after all subjects enrolled in the study have completed Week 13 disease assessment or have discontinued study, whichever is early.

The best overall response will be derived for each subject based on timepoint-wise disease assessments, according to the response categories ordered as CR > PR > SD > PD > NE (Not evaluable). Each subject will be assigned a "best overall response" based on the above-mentioned rule.

Unless otherwise specified, "Baseline" refers to the last non-missing observation before the first administration of study drug.

9.2 Handling of Missing Data

Details on the handling of missing data are described in the analysis section corresponding to each endpoint.

9.3 Primary Efficacy Endpoint and Analyses

9.3.1 Primary Efficacy Endpoint

The primary efficacy endpoint is the best overall response of CR based on IRC assessment and will be evaluated using complete response rate (CRR), defined as proportion of subjects achieving best overall response of CR.

Subjects in PP population but have no post-baseline disease assessment will be considered as non-responders in the calculation of CRR. Subjects who have not achieved best overall response of CR at the time of analysis will be considered as non-responders in the calculation of CRR.

9.3.2 Main Analysis of Primary Efficacy Endpoint

The attributes of the estimand corresponding to the primary efficacy endpoint are summarized in [Table 1](#).

Table 1. Summary of the Estimand Attributes of the Primary Efficacy Endpoint

Attributes of the Estimand					
Estimand Label	Treatment	Population	Endpoint	Handling of Intercurrent events	Statistical Summary
CRR	Venetoclax + Ibrutinib combination for a maximum of 104 weeks followed by Ibrutinib monotherapy until PD	PP population	IRC-assessed best overall response of CR	ICE1: Study drug discontinuation ICE2: Use of other anti-MCL treatment All data will be used regardless of ICE1 or ICE2.	CRR and 95% CI

The analysis of CRR will be based on exact binomial distribution.

9.3.3 Sensitivity and Supplementary Analyses of the Primary Efficacy Endpoint

A sensitivity analysis of best overall response of CR will be performed based on investigator's assessment.

9.4 Secondary Efficacy Endpoints and Analyses

9.4.1 Secondary Efficacy Endpoints

The secondary endpoints (except for MRD and OS) will be assessed according to the Revised Criteria for Response Assessment (Cheson 2014)¹. Endpoint of best overall response of CR or PR will be evaluated using overall response rate (ORR). ORR is defined as the proportion of subjects with a best overall response of CR or PR. This endpoint is assessed separately per IRC and investigator's assessment.

DOT of CR is defined as the time from the first occurrence of response of best overall response of CR to disease progression or death, whichever occurs first. If a subject is still responding, subjects will be censored at the date of the last adequate disease assessment.

DOOR of CR or PR is defined as the time from the first occurrence of best overall response of CR or PR to disease progression or death, whichever occurs first. If a subject is still responding, subjects will be censored at the date of the last adequate disease assessment.

DOOR (of CR, of CR or PR) analyses will be performed separately for IRC and investigator assessed responses.

Endpoint of undetectable MRD (uMRD) is defined as subject achieving uMRD (defined as subjects having < 0.05% MCL cells per 10,000 leukocytes) and a best overall response of CR. MRD will be assessed by flow cytometry of peripheral blood sample per central laboratory for all subjects. The proportion of subjects with undetectable MRD who achieve a best overall response of CR will be provided, separately for IRC and investigator assessed CR.

Progression-free survival is defined as the time from the date of the first dose of any study drug (venetoclax or ibrutinib) to the date of investigator-assessed disease progression, or death from any cause, whichever occurs first. All events of disease progression will be included, regardless of whether the event occurred while the subject was still taking study drug or after the subject discontinued study drug. If the subject does not experience disease progression or death, then the data will be censored at the date of the last adequate disease assessment. Data for subjects without any disease assessments performed after the baseline visit will be censored at the date of the first dose.

Overall survival is defined as the time from the date of the first dose of any study drug (venetoclax or ibrutinib) to death from any cause. All events of death will be included, regardless of whether the event occurred while the subject was still taking study drug or after the subject discontinued study drug or the subject was on other anti-MCL treatment. If a subject has not died, then the data will be censored at the date the subject was last known to be alive.

9.4.2**Main Analyses of Secondary Efficacy Endpoints**

The attributes of the estimands corresponding to the secondary efficacy endpoints are summarized in [Table 2](#).

Table 2. Summary of the Estimand Attributes of the Key Secondary Efficacy Endpoints

Attributes of the Estimand					
Estimand Label	Treatment	Population	Endpoint	Handling of Intercurrent Events	Statistical Summary
Best overall response	Venetoclax + Ibrutinib combination for a maximum of 104 weeks followed by Ibrutinib monotherapy until PD	PP population/FAS, as appropriate	Investigator-assessed best overall response of CR. IRC-assessed best overall response of CR or PR	ICE1: Study drug discontinuation ICE2: Use of other anti-MCL treatment All data will be used regardless of ICE1 or ICE2.	CRR and 95% CI ORR and 95% CI
uMRD		PP population/FAS, as appropriate	Undetectable MRD for a subject with IRC-assessed BOR of CR Undetectable MRD for a subject with investigator-assessed BOR of CR		uMRD rate and 95% CI
DOR		PP population/FAS, as appropriate	IRC-assessed DOR of CR, DOR of CR or PR Investigator-assessed DOR of CR, DOR of CR or PR		K-M estimate at specified time-points and their corresponding 95% CI Median DOR and 95% CI KM curve

Attributes of the Estimand					
Estimand Label	Treatment	Population	Endpoint	Handling of Intercurrent Events	Statistical Summary
PFS		PP population/FAS, as appropriate	Investigator-assessed PFS		K-M estimate at specified time-points and their corresponding 95% CI Median PFS and 95% CI KM curve
OS		FAS	OS		K-M estimate at specified time-points and their corresponding 95% CI Median OS and 95% CI KM curve

The analysis of CRR, ORR and uMRD rates will be based on exact binomial distribution.

The analysis of DOR, PFS and OS will be based on Kaplan-Meier methodology.

9.4.3 Supportive Secondary Efficacy Analyses

Not applicable.

10.0 Safety Analyses

10.1 General Considerations

Safety data will be summarized for the Full Analysis Set defined in Section 4.0.

10.2 Adverse Events

Adverse events (Aes) will be summarized and presented using primary MedDRA System Organ Classes (SOCs) and preferred terms (PTs) according to the version of the MedDRA

coding dictionary used for the study at the time of database lock. The actual version of the MedDRA coding dictionary used will be noted in the AE tables and in the clinical study report. Specific adverse events will be counted once for each subject for calculating percentages, unless stated otherwise. In addition, if the same adverse event occurs multiple times within a subject, the highest severity and level of relationship to investigational product will be reported.

10.2.1 Treatment-Emergent Adverse Events

Treatment-emergent AEs are defined as any AE with the onset that is after the first dose of study drug until 30 days after the last dose of the study drug for subjects. Events where the onset date is the same as the study drug start date are assumed to be treatment-emergent. If an incomplete onset date was collected for an AE, the AE will be assumed to be treatment-emergent unless there is evidence that confirms that the AE was not treatment-emergent (e.g., the AE end date was prior to the date of the first dose of study drug).

For summaries of AEs related (reasonable possibility) to study drug, at each level of summation (overall, SOC, and PT) each subject is counted only once. If a subject has an AE with unknown relationship, then the subject will be counted in the relationship category of "unknown," even if the subject has another occurrence of the same event with a relationship of "no reasonable possibility" present. The only exception is if the subject has another occurrence of the same AE with the relationship of "reasonable possibility." In this case, the subject will be counted under the reasonable possibility category.

All treatment-emergent AEs will be summarized overall, as well as by primary MedDRA SOC and Preferred Term. The SOCs will be presented in alphabetical order, and the PTs will be presented in alphabetical order within each SOC.

The number and percentage of subjects experiencing treatment-emergent AEs will be summarized.

10.2.2 Adverse Event Overview

An overview of AEs will be presented consisting of the number and percentage of subjects experiencing at least one event for each of the following AE categories:

- Any treatment-emergent adverse event
- Any treatment-emergent adverse event with NCI toxicity (CTCAE version 4.03) grade 3, adverse events
- Any treatment-emergent adverse event with NCI toxicity (CTCAE version 4.03) grade 4 adverse events
- Any treatment-emergent adverse event with NCI toxicity (CTCAE version 4.03) grade 5 adverse events
- Any treatment-emergent adverse event with NCI toxicity (CTCAE version 4.03) grade 3 or 4 adverse events
- Any treatment-emergent adverse events leading to DLT
- Any treatment-emergent adverse events related to COVID-19 infection
- Any treatment-emergent adverse event leading to discontinuation of venetoclax
- Any treatment-emergent adverse event leading to venetoclax interruption
- Any treatment-emergent adverse event leading to venetoclax reduction
- Any treatment-emergent adverse event that is rated at least possibly related to venetoclax by the investigator (Reasonable Possibility Related)
- Any treatment-emergent adverse event leading to discontinuation of ibrutinib
- Any treatment-emergent adverse event leading to ibrutinib interruption
- Any treatment-emergent adverse event leading to ibrutinib reduction
- Any treatment-emergent adverse event that is rated at least possibly related to ibrutinib by the investigator (Reasonable Possibility Related)
- Any treatment-emergent serious adverse event
- Any treatment-emergent adverse event leading to death

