7.4 Statistical Analyses for Safety

The safety and tolerability of venetoclax in combination with ibrutinib will be assessed by evaluation of study drug exposure, DLTs, AEs, SAEs, and deaths, as well as changes in laboratory parameters, physical examinations, electrocardiogram (ECG), and vital sign measurements.

Tolerability of venetoclax and ibrutinib combination will be assessed for the first 6 evaluable subjects, where an evaluable subject is defined as a subject who has received the combination for a minimum of 5 weeks and at least 1 week of venetoclax dosed at 400 mg.

Details on the statistical analyses for safety are provided in the SAP.

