2.2 Study Design Overview

This Phase 2, open-label, single-arm study is designed to evaluate the efficacy and safety of the combination of venetoclax and ibrutinib in Japanese subjects with R/R MCL.

Approximately 12 subjects will receive ibrutinib at 560 mg once daily until progression and venetoclax starting at 20 mg once daily and gradually ramped up to a target dose of 400 mg once daily over a 5-week period for a maximum period of 104 weeks.

[figure not shown]
Dose-limiting toxicities will be evaluated in the first 6 subjects, from Day 1 for a minimum of 5 weeks and at least 1 week of venetoclax dosing at 400 mg, in order to confirm the initial safety and tolerability in Japanese subjects. After the completion of the DLT evaluation period in the first 6 subjects, the AbbVie Study Team and investigators who enrolled the 6 treated subjects will review all available safety and PK data to evaluate the tolerability of venetoclax in combination with ibrutinib in Japanese subjects with R/R MCL. If there are zero or 1 DLTs in the first 6 subjects, enrollment of the additional 6 subjects will proceed. If DLTs are observed in 2 or more of the first 6 subjects, further enrollment in Japan will be interrupted and additional, a detailed safety assessment will be conducted.

A DLT is defined as any Grade ≥ 3 adverse events considered to be at least possibly related to study drug (ibrutinib and/or venetoclax) and occurring during the DLT assessment period as defined in protocol Section 6.3. Under certain circumstances as defined in protocol Section 6.3, a subject is not evaluable for DLT, that subject will be replaced but are included for efficacy analysis.

Subjects who discontinue study treatment for any reason will be followed for progression (if no progression before treatment discontinuation), subsequent anti-cancer therapy, and survival status until study closure, as appropriate

The schematic of the study is shown in [Figure 1](#).

Figure 1. Study Schematic

FU = follow up; MCL = mantle cell lymphoma; PD = disease progression; R/R = relapsed/refractory; wks = weeks

Note: After approval of venetoclax and ibrutinib combination therapy for R/R MCL in Japan, Study M20-075 will be discontinued, and subjects will transition to commercial drug.

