2.4 Sample Size Determination

Approximately 12 subjects will be enrolled in the study. The tolerability of the combination of venetoclax and ibrutinib will be assessed after the first 6 subjects enrolled

in the study have received the combination for a minimum of 5 weeks and at least 1 week of venetoclax dosed at 400 mg.

Using exact binomial test, with an expected complete response rate (CRR) of 50% for venetoclax in combination with ibrutinib and a threshold CRR of 12.5%, 12 subjects will provide 80% power to demonstrate superiority of venetoclax in combination with ibrutinib against a historical reference of 12.5% CRR in the ibrutinib only Japanese study with R/R MCL, at a 1-sided overall significance level of 0.025. A significant test result is achieved when at least 5 CRs are observed among 12 subjects, corresponding to a minimal observed CRR of 41.7%.

If the first 12 subjects include one or more subjects who are assessed by the IRC as non-evaluable at baseline, then additional subject(s) will be enrolled at the Sponsor's discretion to ensure that there are 12 evaluable subjects per IRC assessment for primary endpoint analysis.

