4.0 Analysis Populations

The following population set will be used for the analyses:

The full analysis set (FAS) includes all subjects who received at least 1 dose of study drug. The FAS will be used for all efficacy (except the endpoints based on IRC assessment), safety, pharmacokinetic, and baseline analyses.

The per protocol (PP) population excludes FAS subjects who have been determined as having non-evaluable disease at baseline, based on IRC assessment. PP population will be used for IRC assessed endpoints. PP population will be used to compare the sensitivity of IRC endpoints with investigator assessed endpoints.

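### The DLT row of the SAP's adverse event overview defaults to all treated subjects, although DLTs are assessed only in the first six evaluable subjects

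*SAP*

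**What the plan says.** SAP 10.2.2 describes the overview table: "An overview of AEs will be presented consisting of the number and percentage of subjects experiencing at least one event" in each of 17 listed categories. One category is "Any treatment-emergent adverse events leading to DLT". No category is given a denominator of its own.

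SAP 10.1 supplies the general rule: "Safety data will be summarized for the Full Analysis Set defined in Section 4.0". SAP 4.0 then defines two sets. For the first, "The full analysis set (FAS) includes all subjects who received at least 1 dose of study drug". The second, the per protocol population, removes FAS subjects whose disease the independent review committee found non-evaluable at baseline, which has nothing to do with DLTs. There is no DLT-evaluable set.

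On the size of the FAS, SAP 2.4 says "Approximately 12 subjects will be enrolled in the study". It also provides that if the committee finds some of the first 12 non-evaluable at baseline, "then additional subject(s) will be enrolled at the Sponsor's discretion to ensure that there are 12 evaluable subjects" for the primary analysis, so the FAS may exceed 12.

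On who is assessed for DLTs, SAP 2.2 says "Dose-limiting toxicities will be evaluated in the first 6 subjects, from Day 1 for a minimum of 5 weeks", and protocol 7.4 says "Tolerability of venetoclax and ibrutinib combination will be assessed for the first 6 evaluable subjects". Protocol 6.3 and SAP 2.2 count an event as a DLT only if it falls in the DLT assessment period, which belongs to those first six. SAP 2.2 proceeds to the remaining enrolment on zero or one DLT among them and interrupts it on two or more.

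**The concern.** A subject enrolled after the DLT cohort is complete has no DLT assessment period and so cannot record a DLT. Such a subject contributes nothing to the numerator of the row but adds one to its denominator. The percentage then treats not having been assessed as having been assessed and found free of DLTs, and the error can only run in the favourable direction.

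DLTs are the first item named under the safety endpoints in protocol 3.4 and SAP 3.4. Protocol 7.4 leaves the details of the safety analysis to the SAP. SAP 12.0 and 12.1 describe a tolerability review of the first six evaluable subjects but specify no statistic or table for it. The row in 10.2.2 is therefore the only DLT summary whose output the SAP specifies, and its denominator differs from the one protocol 7.4 uses for tolerability.

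**Working it through.** **Inputs**
- Statistic for the row: count and percentage of subjects (SAP 10.2.2).
- Default safety denominator: FAS (SAP 10.1 and 4.0).
- Planned FAS size: about 12, possibly more (SAP 2.4).
- Subjects assessed for DLTs: 6 (SAP 2.2; protocol 6.3 and 7.4).
- Number of DLTs, d: not given. SAP 9.1 reports only the recommendation to continue to full enrolment.

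**The plan's own figure.** The documents state no DLT percentage, so there is none to reproduce. The figure behind the planned 12 is the sample size statement, and it does reproduce. With 12 subjects, a cutoff of 5 complete responses, a threshold of 12.5% and an expected rate of 50%, exact power is 0.806 against the stated 80%. The exact one-sided type I error is 0.0113. A cutoff of 4 would give 0.0528, so 5 is the right cutoff. This confirms 12 as the planning size and has no bearing on the DLT denominator.

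**Formulas**
- Percentage in the table as written: d / N_FAS.
- Proportion among those assessed: d / 6.
- Ratio of the first to the second, for d of 1 or more: 6 / N_FAS.

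**Results at the planned FAS of 12** (ratio 6/12 = 0.50)

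| DLTs | Table as written | Among the six assessed |
|---|---|---|
| 0 | 0/12 = 0% | 0/6 = 0% |
| 1 | 1/12 = 8.3% | 1/6 = 16.7% |
| 2 | 2/12 = 16.7% | 2/6 = 33.3% |

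**Other FAS sizes (assumed).** The ratio is 6/10 = 0.60, 6/13 = 0.46, 6/14 = 0.43 and 6/15 = 0.40. One DLT would then show as 10.0%, 7.7%, 7.1% and 6.7%.

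**Replaced subjects (assumed numbers).** Protocol 6.3 replaces non-evaluable subjects and keeps them within the planned 12. If one or two subjects were dosed and replaced, and the denominator were everyone dosed in the DLT cohort, one DLT would be 1/7 = 14.3% or 1/8 = 12.5%. Both are still above the 8.3% in the table as written.

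**Can the right denominator be derived from the text?** Not without a decision, because the passages differ:
- SAP 9.1 refers to the first six enrolled; protocol 7.4 and SAP 12.0 refer to the first six evaluable.
- Protocol 6.3 makes a non-completer non-evaluable only if the reason is something other than a DLT.
- Protocol 7.4, and a further sentence in 6.3, require five weeks on treatment or study and one week of venetoclax at 400 mg. Read literally, that drops a subject who stops early because of a DLT.
- Protocol 6.3 bases the tolerability decision on everyone dosed, whether DLT-evaluable or not.

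**The case against.** The best defence is that the tolerability question is answered elsewhere, on the right subjects. The enrolment rule is a count among the first six, an independent safety monitor reviews it, and SAP 9.1 records that the review is over and enrolment continued. The row in 10.2.2 is one of 17 descriptive categories, drives no test, and prints the count beside the percentage. The SAP also does not say in so many words that this row uses the FAS; that follows from the general rule in 10.1. All of this stands, and it limits the point to reporting. It does not remove it, because the general rule has no exception and SAP 4.0 offers no suitable set.

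Several stronger readings are tempting, and the documents do not support them:
- A reader might infer that the table reports half the true DLT rate. The proportion d/6 is a sample proportion from six subjects, not a true rate. The halving needs a FAS of about 12 and at least one DLT, and the count is not given.
- A reader might infer that the trial's formal tolerability result is distorted. That result is the count in the first six.
- A reader might infer overstated precision. The SAP plans no confidence interval for this row.
- A reader might set the percentage against the parent study's run-in, where 3 of 21 had DLTs (14.3%). Neither document plans that comparison.
- A reader might infer that no subject enrolled seventh or later can have a DLT. A replacement subject enrolled later can belong to the DLT cohort.

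**Conclusion.** The point holds as a reporting defect. Followed as written, SAP 10.1 and 10.2.2 give a DLT percentage whose denominator includes subjects who were never assessed for DLTs. At the planned FAS of 12 with six assessed, any non-zero percentage is half the proportion among those assessed (8.3% against 16.7% for one DLT). The understatement grows if the FAS exceeds 12 and vanishes if there were no DLTs.

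This rests on two assumptions: that the general rule in 10.1 governs the row, and that about half the treated subjects fall outside the DLT cohort. It is more than missing detail, because the stated rule itself produces the misleading figure. The enrolment decision and the primary analysis are not affected.

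**What to change.** 1. Add a DLT-evaluable set to SAP 4.0 that follows protocol 6.3, so that a subject who stops early because of a DLT stays in it. Reconcile it with the literal five-week and one-week-at-400-mg wording in protocol 6.3 and 7.4, and with the differing references to enrolled and evaluable subjects.
2. Report the DLT row of 10.2.2 as n/N with N equal to that set.
3. List subjects who were dosed in the DLT cohort but replaced separately, with any events they had, since protocol 6.3 uses their data in the tolerability decision.
4. Footnote the remaining subjects as not assessed for DLT.

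The cost is one definition and one table footnote, with no new data. Any non-zero percentage becomes less favourable. Protocol Appendix J states that the primary analysis is complete, so the change applies to the final report or a re-issued table.
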